10.6. Assessment of Safety

Retrospective data collection will include the collection and recording of device and procedure-related AEs which occurred from the time of implant until present day. No safety reporting to IRBs will be executed for retrospective events. AEs found via the retrospective chart review will be reported to Medtronic Product Quality Experience Group as required by regulations.

Prospective data collection will be from the date of signed IC, and will be reported to Medtronic's Product Quality Experience Group and the IRBs per Institutional reporting requirements.

10.7. Recording Data

Data will be recorded on electronic Case Report Forms (eCRFs) in the Electronic Data Capture (EDC) system, Oracle Clinical. For the retrospective portion of the study medical charts, operative notes, and other medical records will be considered as the source documents. For the prospective portion of the study, CRFs can be used as source for this study as well as medical charts. Source document worksheets will be provided to the sites if requested.

10.8. Deviation Handling

It is expected that the Investigator will adhere to the protocol and not deviate unless medically necessary in response to an emergency situation to protect the rights, safety and well-being of the subject.

Planned deviations may be submitted to the Sponsor in advance for review and approval, as necessary. Protocol deviations that occur will be documented on the Protocol Deviation CRF and reported to the IRB based on the IRB schedule.

This document is electronically controlled. Printed copies are considered uncontrolled.

Confidential

10.9. Subject Withdrawal or Discontinuation

If a subject is consented but subsequently decides to withdraw from the study before coming in for the prospective data collection visit, the subject will be considered to be withdrawn from the study, and the reason will be captured on the Study Exit CRF.

Subjects who are unresponsive after a minimum of 3 attempts to contact them by phone or other means for their prospective data collection visit will be considered lost to follow-up. The types of attempts (phone, email, text, mail) will also be captured on the Study Exit CRF. Note: retrospective safety data collected may still be used in the study.

11. Risks and Benefits

11.1. Potential Risks

The risks for this study are minimal. Risks inherent to use of the Sophono system or surgical procedure are outlined in the potential AEs found in Section 12.

11.2. Potential Benefits

There may not be any direct medical benefits to the study subjects. This study will help the Sponsor evaluate the safety and effectiveness of the hearing system to develop future products to assist others with similar hearing impairment. Subjects will be reimbursed for their participation.

11.3. Risk-Benefit Rationale

As the risks to this study are minimal (limited to subject inconvenience), the benefits of the increased data portfolio on the safety and processor effectiveness outweigh the associated risks.

12. Adverse Event Assessments

12.1. Definitions/Classifications

The below definitions are standard ISO regulation definitions required for all Medtronic studies. These definitions are given with the understanding that the Sophono device is an approved device and not considered investigational.

Adverse Event (ISO 14155:2011, 3.2)	
Any untoward medical occurrence, unintended disease or injury, or untoward clinical signs (including abnormal laboratory findings) in subjects, users or other persons, whether or not related to the investigational medical device.
 
Note: This definition includes events related to the investigational medical device or the comparator.
 
Note: This definition includes events related to the procedures involved.
 
Note: for users or other persons, this definition is restricted to events related to investigational medical devices.

Adverse Device Effect (ADE) (ISO 14155:2011, 3.1)	
Adverse event related to the use of an investigational medical device.
 
Note: This definition includes adverse events resulting from insufficient or inadequate instructions for use, deployment, implantation, installation, or operation or any malfunction of the investigational medical device.
 
Note: This definition includes any event resulting from use error or from intentional misuse of the investigational medical device.

Serious Adverse Event (SAE) (ISO 14155:2011, 3.37)	
Adverse event that:
 
a) Led to a death,b) Led to a serious deterioration in the health of the subject, that either resulted in:1) Resulted in a life threatening illness or injury, or

This document is electronically controlled. Printed copies are considered uncontrolled.

Confidential

	
2) Resulted in a permanent impairment of a body structure or a body function, or
 
3) In-patient or prolonged hospitalization, or
 
4) Medical or surgical intervention to prevent life threatening illness or injury or permanent impairment to a body structure or a body function, or Led to fetal distress, fetal death or a congenital abnormality or birth defect.
 
Note: Planned hospitalization for a pre-existing condition, or a procedure required by the CIP, without serious deterioration in health, is not considered a serious adverse event.

Serious Adverse Device Effect (SADE)
 
(ISO 14155:2011, 3.36)
	
Adverse device effect that has resulted in any of the consequences characteristic of a serious adverse event.

Information regarding any reportable AEs and outlined in Tables 4 & 5 below, in relation to the device or the procedure (as determined by the Investigator) that occur during the study will be recorded. This information will include, at a minimum, the date of the event, the seriousness of the event (prospective), the severity, actions taken, the outcome, and the relationship (if any) of the event to the device. Subject continuation in the study as prescribed in this protocol following an AE is anticipated, unless determined otherwise by the Investigator.

12.1.1. Classification of adverse events

SEVERITY OF EVENT

All AEs will be assessed by the clinician using the following guidelines to describe severity.

- **Mild** – Events require minimal or no treatment and do not interfere with the participant's daily activities.
- **Moderate** – Events result in a low level of inconvenience or concern with the therapeutic measures. Moderate events may cause some interference with functioning.
- **Severe** – Events interrupt a participant's usual daily activity and may require systemic drug therapy or other treatment. Severe events are usually potentially life-threatening or incapacitating.

This document is electronically controlled. Printed copies are considered uncontrolled.

Confidential

RELATIONSHIP OF DEVICE

The clinician's assessment of an AE's relationship to study device is part of the documentation process, but it is not a factor in determining what is or is not reported in the study. If there is any doubt as to whether a clinical observation is an AE, the event should be reported. All AEs must have their relationship to study device assessed. In a clinical trial, the study product must always be suspect. To help assess, the following guidelines are used.

Not related: relationship to the device or procedures can be excluded when:

- the event is not a known side effect of the product category the device belongs to or of similar devices and procedures;
- the event has no temporal relationship with the use of the investigational device or the procedures;
- the serious event does not follow a known response pattern to the medical device (if the response pattern is previously known) and is biologically implausible;
- the discontinuation of medical device application or the reduction of the level of activation/exposure - when clinically feasible – and reintroduction of its use (or increase of the level of activation/exposure), do not impact on the serious event;
- the event involves a body-site or an organ not expected to be affected by the device or procedure;
- the serious event can be attributed to another cause (e.g. an underlying or concurrent illness/ clinical condition, an effect of another device, drug, treatment or other risk factors);
- the event does not depend on a false result given by the investigational device used for diagnosis, when applicable;
- harms to the subject are not clearly due to use error;
- In order to establish the non-relatedness, not all the criteria listed above might be met at the same time, depending on the type of device/procedures and the serious event.

Unlikely: the relationship with the use of the device seems not relevant and/or the event can be reasonably explained by another cause, but additional information may be obtained.

Possible: the relationship with the use of the investigational device is weak but cannot be ruled out completely. Alternative causes are also possible (e.g. an underlying or concurrent illness/ clinical condition or/and an effect of another device, drug or treatment). Cases where relatedness cannot be assessed or no information has been obtained should also be classified as possible.

Probable: the relationship with the use of the investigational device seems relevant and/or the event cannot reasonably explained by another cause, but additional information may be obtained.

Causal relationship: the serious event is associated with the investigational device or with procedures beyond reasonable doubt when:

- the event is a known side effect of the product category the device belongs to or of similar devices and procedures;
- the event has a temporal relationship with investigational device use/application or procedures;
- the event involves a body-site or organ that
 - the investigational device or procedures are applied to;
 - the investigational device or procedures have an effect on;
- the serious event follows a known response pattern to the medical device (if the response pattern is previously known);
- the discontinuation of medical device application (or reduction of the level of activation/exposure) and reintroduction of its use (or increase of the level of activation/exposure), impact on the serious event (when clinically feasible);
- other possible causes (e.g. an underlying or concurrent illness/ clinical condition or/and an effect of another device, drug or treatment) have been adequately ruled out;
- harm to the subject is due to error in use;
- the event depends on a false result given by the investigational device used for diagnosis, when applicable;
- In order to establish the relatedness, not all the criteria listed above might be met at the same time, depending on the type of device/procedures and the serious event.

Where the relationship remains uncertain, it should not exclude the relatedness and the event should be classified as "possible".

EXPECTEDNESS

An anticipated adverse event is defined as an AE, the nature, severity, or degree of incidence of which is known and identified in applicable product labeling, published literature or the Investigational Plan or Informed Consent.

Based on event reports through literature review (15-19) anticipated Surgical Related AE's possibly noted in the Operative Report during the retrospective medical chart review should be reported on the appropriate CRF. These events may include:

This document is electronically controlled. Printed copies are considered uncontrolled.

Confidential

Table 4. Surgical Related Adverse Events

Event
Excessive Bleeding
Rupture of Dura
Cerebrospinal Fluid (CSF) Leak
Anesthesia Related Complications

Anticipated Post-operative Related AE's possibly seen in the retrospective medical chart review or at the office visit and their reportability within the study may include:

Table 5. Post-Operative Related Adverse Events

Event	Reportable Criteria
Abscess	Requiring medical intervention
Bleeding	Requiring medical intervention
Dehiscence (at Incision Site)	Requiring medical intervention
Depilation (Loss of Hair at Implant Site)	Excessive or cosmetically bothersome
Hematoma	Requiring medical intervention
Hyperemia	Excessive or requiring medical intervention
Infection (i.e. Cellulitis, Bacterial, etc.)	Requiring medical intervention
Inflammation/Skin Irritation (Redness)	Holger 2, 3, 4
Numbness (Hypoesthesia)	Notable or bothersome to subject

This document is electronically controlled. Printed copies are considered uncontrolled.

Confidential

Pain (Local)	Prolonged surgical procedure pain or pain lasting more than 10 days
Pressure (at the Implant Site)	Feeling of pressure continuing after subject begins using the processor
Scarring	Abnormal or Hypertrophic
Skin Necrosis (Pressure)	Requiring medical intervention
Swelling	Continuing after subject begins using the processor

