8.1. General

The Sophono Bone Conduction Hearing Systems are a family of sound processors and accessories that operate on the principle of BC of sound vibrations. The Sophono Bone Conduction Hearing Systems

This document is electronically controlled. Printed copies are considered uncontrolled.

Confidential

transmits audio vibrations through the skin into the bone where sound is sensed by the inner ear/cochlea.

The Sophono Sound Processor is magnetically attracted to the Magnetic Implant and Magnetic Spacer. The Magnetic Implant, which is secured to the skull bone, affixes the Magnetic Spacer to the head transcutaneously through magnetic attraction forces, and the Sound Processor is magnetically affixed to the Magnetic Spacer. Vibration from the Sound Processor is transduced through the Magnetic Spacer to the Magnetic Implant and through the bone to the inner ear.

Figure 1 Sophono Bone Conduction Hearing System

The Magnetic Implant is the same size and configuration for all subjects, regardless of the processor. The Attract® Magnetic Spacer comes in various strengths. The appropriate strength for daily wear is recommended by the Audiologist at the time of processor optimization. The results of the hearing tests with these magnets are out of scope of this study.

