10.1. Schedule of Events

After proper administration and signing of the IC and Research Authorization Forms, all potential subjects will be assessed for study eligibility based on the Inclusion and Exclusion Criteria. Inclusion and Exclusions data as well as limited demographic information will be captured in the subject CRFs.

A ***retrospective review*** of the subject's medical chart will be performed to gather and report data on subject surgical history, reportable AEs from the time of implantation to time of chart review, previous QOL scores, and previous audiometric testing results for Alpha 2 and/or Alpha 2 MPO processors.

An ***in-office visit*** will be conducted with an ENT physician and Audiologist, ideally on the same day, where the following assessments will take place:

ENT Visit:

The ENT visit will consist of an examination of the ear and implant site for skin complications (according to the *Holger Skin Evaluation Index* in Table 2) or other potential AEs (see Section 12 for reportable AEs). The ENT Visit CRF will detail findings (such as erythema, scar, etc.) as well as complications (skin loss, infection, etc.). Any such complications will be recorded on an AE form.

Sophono system satisfaction and QOL questions shall also be administered to allow the subjects' perceived benefits to be assessed. The QOL assessment will be done using the APHAB Version A.

Table 2. Holger Skin Evaluation Index

The skin directly over the implant site will be evaluated on the Holger Skin Evaluation Index.

Holger Skin Evaluation Index
0 = No irritation. Epithelium debris removed if present.
1 = Slight redness, local treatment.
2 = Red and slightly moist tissue. No granuloma formation noted. Local treatment. Extra controls.
3 = Status as in 1 and 2 but local revision became necessary.
4 = Removal of skin-penetrating implant necessary due to infection.
R = Removed implant for reasons not related to skin problems.

Audiology Visit:

All audiometric testing equipment should be calibrated and tested to American National Standards Institute (ANSI) standards, in good repair and functioning well.

All tests should be performed in the order presented in Table 3. Subject will be blinded to processor order.

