7.10.1 Primary endpoint

The primary safety endpoint is the proportion of AEs related to the Sophono implant or surgery, which will be assessed through retrospective surgical chart review and prospective ENT exam. The primary safety endpoint will be evaluated on FAS. The AEs used for this endpoint are according to Investigator's determination of the event's relatedness to the device or surgery.

Adverse Event rates will be displayed together with their 95% confidence interval (95%CI) overall, by site and by type of event.

A time to first Adverse Event will be performed using survival analysis. The analysis will be supported by a Kaplan Meier curve indicating the number of patients at risk and any possible comparison of curves between groups will be done using the Log-Rank Test where appropriate.

Table x - Primary safety endpoint – Sophono Implant related Adverse Events rates

Figure x - Kaplan Meier estimate of first Sophono Implant related Adverse Event occurrence

Table x - Kaplan Meier estimate of first Sophono Implant related Adverse Event occurrence

The primary effectiveness endpoint is the absolute difference (gain) in the free-field pure tone audiometry assessed by PTA unaided (AC) and aided by the Alpha 2 MPO processor. The primary effectiveness endpoint will be evaluated on PPS.

The difference between unaided and aided measurements will be analyzed by means of paired (samples) t-test or Wilcoxon signed rank sum test according to the normal or non-normal distribution.

Additional analysis will be performed on:

- the "within indication" subset will exclude from the analysis subjects whose Prospective AC & BC tests do not meet the device indications for use.

- The subsets defined by implanted ear diagnosis. For the subject affected by SSD, analyses will be performed for both the derived variables (both NR substitution methods).

Table x - Primary effectiveness endpoint - Difference in PTA between unaided (AC) and aided by the alpha 2 MPO Processor (Audiogram Results Gain)

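### The Table 5 criterion for implant-site pressure and swelling cannot capture symptoms that delay or prevent processor use, is unclear for onset with magnet wear, and conflicts with the broader AE recording rules behind the primary safety endpoint

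*Protocol*

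**What the plan says.** Protocol 12.1.1, Table 5, pairs each anticipated post-operative event with a reportable criterion. For pressure at the implant site it is "Feeling of pressure continuing after subject begins using the processor". The swelling row uses the same condition, "continuing after subject begins using the processor". Neither row mentions symptoms that start later, or subjects who do not start the processor.

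Two sets of passages say what is recorded.

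- **Narrower.** Protocol 12.1 describes what is recorded as "Information regarding any reportable AEs and outlined in Tables 4 & 5 below, in relation to the device or the procedure". Protocol 10.1 limits chart review to "reportable AEs from the time of implantation to time of chart review", and SAP 5.3 repeats that scope. For the ENT visit, Protocol 10.1 refers to Section 12 for what is reportable.
- **Broader.** Protocol 10.6 collects device- and procedure-related AEs from implant onwards. Protocol 12.2 records every AE related to surgery or device at chart review, and at the visit asks about AEs without restriction.

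SAP 7.10.1 states: "The primary safety endpoint is the proportion of AEs related to the Sophono implant or surgery". Relatedness is the investigator's judgement, and rates are shown overall, by site and by event type. Protocol 6.2.1.1 defines the endpoint in similar terms. Neither definition refers to Table 5 or to the rule in 12.2.

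**The concern.** The evident purpose of the two rows is to screen out ordinary post-surgical pressure and swelling that settles before the processor is worn. The condition chosen is first processor use, and that suits this device poorly. According to Protocol 8.1, the implant "affixes the Magnetic Spacer to the head transcutaneously through magnetic attraction forces", so local pressure is a plausible effect of the magnet itself. Protocol 5.1 also reports skin reactions that resolved once magnet force was adjusted.

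A symptom severe enough to keep the subject from wearing the processor never meets a condition that begins with processor use. Such subjects are in scope: Protocol 9.3 admits explanted patients and does not require processor use. Protocol 7 reserves the prospective visit for subjects still implanted, so for explanted subjects chart review is the main source, and 10.1 restricts it to reportable AEs.

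A primary endpoint is at stake. An event that a site does not record cannot enter the numerator, and by-site rates are not comparable if sites follow different rules.

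**Working it through.** **1. The criterion applied to four illustrative records.** The word *continuing* has two fair readings. Reading A: the symptom began before processor use and outlasted its start. Reading B: the symptom persists during use, whenever it began.

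| Record | Onset | Processor start | End | A | B |
|---|---|---|---|---|---|
| 1 | day 7 | day 30 | day 60 | met | met |
| 2 | day 45, with magnet wear | day 30 | day 120 | not met | met |
| 3 | day 3 | never | day 150 | not met | not met |
| 4 | day 3 | day 30 | day 20 | not met | not met |

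Record 4 is the transient case that the rows are meant to screen out. Record 2 depends on the reading, so it shows ambiguity rather than exclusion. Record 3 fails on both readings. Record 4 also has the same date pattern as a subject whose start was postponed until the symptom resolved, so the criterion cannot tell a harmless early symptom from one that held up use. A subject explanted before starting is in the position of record 3.

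**2. The same records under Protocol 10.6 and 12.2.** If judged related to the device or the procedure, all four are recorded. The two rules thus disagree on records 3 and 4 on either reading, and on record 2 under reading A.

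**3. Direction.** For these two rows the narrower rule can only remove events relative to the broader one. Any error from following it therefore lowers the related-AE proportion.

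**4. Scale against the plan's own figure.** Protocol 13.1 assumes 14% incidence, 72 subjects and a 95% interval of +/- 9% (5% to 23%).

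- Wald half-width: 1.96 x sqrt(0.14 x 0.86 / 72) = 8.0%.
- With continuity correction: 8.0% + 1/(2 x 72) = 8.7%, giving 5.3% to 22.7%. This rounds to the stated figure.
- Enrolment: 72 / (1 - 0.25) = 96, stated as about 100.

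The documents give no frequency for the affected events, so no corrected figure can be derived. For illustration, read the endpoint as subjects with at least one related AE, and assume that k subjects have only a missed event:

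| Denominator | k = 0 | k = 1 | k = 5 |
|---|---|---|---|
| 72 | 10/72 = 13.9% | 11/72 = 15.3% | 15/72 = 20.8% |
| 100 | 14/100 = 14.0% | 15/100 = 15.0% | 19/100 = 19.0% |

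Each missed subject costs 1/72 = 1.4 points or 1/100 = 1.0 point. The second row is closer to the planned analysis: SAP 7.1.3 evaluates safety on the FAS, and Protocol 10.4 keeps chart data from subjects who do not attend the visit. The range of 1 to 5 is an assumption.

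**The case against.** The strongest reply is that nothing is actually excluded. Table 5 lists anticipated events, introduced by "at the office visit and their reportability within the study may include", and does not say that other presentations are out. Protocol 12.1.1 tells clinicians to report when unsure whether an observation is an AE. Protocol 10.6 and 12.2 are broad, and the endpoint definitions count related AEs without citing Table 5. Some of these cases would enter through other rows, such as pain beyond 10 days, Holger grade 2 to 4, or skin necrosis needing intervention.

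Much of this stands. A reader might infer that pressure and swelling starting with magnet wear are left out of the primary endpoint. The documents do not support that: neither cell states an onset condition, reading B is as natural as reading A, and a site following 12.2 would record the event.

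Three parts of the reply do not remove the problem. The instruction for doubtful cases concerns whether something is an AE, not whether it meets a listed criterion. The open wording of the list leaves room for unlisted events, but pressure and swelling are listed, each with its own criterion. A feeling of pressure without pain, or swelling without red, moist skin, need not fit any neighbouring row. The breadth of 12.2 is itself one side of the conflict, since nothing says that it prevails over 10.1 and 12.1.

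**Conclusion.** The point holds as a gap in a criterion and an unresolved conflict between recording rules. The two Table 5 rows cannot be met when pressure or swelling prevents processor use, delays it until the symptom has resolved, or leads to explant first. They are ambiguous for onset during magnet wear. Because the governing rule is not named, sites may capture these events differently. Under the narrower rule the primary safety proportion can only be understated.

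The size of any understatement is unknown. A reader might take the illustrative 1.4 to 6.9 points (1/72 to 5/72) as an estimate of bias. It is not one: the number of missed subjects is assumed, and on a denominator of about 100 the same assumption gives 1.0 to 5.0 points. The conclusion on direction assumes only that some sites treat Table 5 as a filter, which Protocol 10.1 and 12.1 permit.

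**What to change.** 1. Reword both Table 5 cells so that pressure or swelling is reportable if it persists or starts during processor use, if it delays or prevents processor use, or if it leads to explant. Symptoms that settle before use begins, without affecting its start, stay outside these two criteria.
2. Reconcile Protocol 10.1, 12.1 and Table 5 with 10.6 and 12.2, and align SAP 5.3.
3. State in Protocol 12.2, and in the endpoint definitions (Protocol 6.2.1.1 and SAP 7.10.1), which rule sets the primary safety numerator, for chart review and visit alike. This should not be done by applying Table 5 as a limit on 12.2. That would narrow its general recording rule for every row of the table and reduce capture.

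The cost is two table cells, a few sentences and one CRF instruction, with no new procedures or subjects. If chart review has already begun, the charts already abstracted would need a second look for these two terms. The downside is a somewhat higher reported AE figure, which may include some mild events during use.
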